**C. RESEARCH DESIGN AND METHODS**

**OVERVIEW**

The first 10-12 participants in the MTG intervention will not be randomized to ensure that the intervention can be implemented within PACT. We will then conduct a randomized, controlled pilot study in the VA NYHHS primary care clinic to test the feasibility of implementation and acceptability of the MOVE! Toward your Goals (MTG) intervention for patients and providers. There are two distinct phases of the randomized intervention: Pilot Phase 1 and Pilot Phase 2. We will assess intermediate (e.g. self-efficacy, goal attainment, motivation to lose weight), behavioral (diet and physical activity) outcomes, and weight loss at 3, 6, and 12 months. Pilot Phase 2 is a continuation of Pilot Phase 1, however the methods of recruitment and sequence of events will be modified to maximize ease and enrollment.

In both phases, we will train participating PACT teamlets and health coaches to facilitate goal setting and conduct motivational interviewing to facilitate goal setting and conduct brief telephone counseling so that they can deliver the intervention. We will recruit primary care patients and randomize to either receive the MTG intervention or Enhanced Usual Care. On the first Baseline study visit, all participants will complete a Baseline Survey and obtain weight and height measurements.

Those in the MTG intervention group will then complete the MTG tool on a tablet computer, receive a binder of personalized materials generated by the tool, and receive a 15-20 minute counseling session about weight loss and lifestyle goals with a Health Coach (research team member). Participants randomized to the Enhanced Usual Care control will receive a handout about local MOVE!

programs and selected VA MOVE! and Healthy Living Message handouts related to weight management.

After this Baseline study visit, participants in the MTG intervention group will receive 10-15 follow up counseling phone calls with the health coach to review goals over a 12 month period. In Pilot Phase 1, participants will meet with their PCP during their regularly scheduled visit before taking an exit survey. In Pilot Phase 2, participants will meet with their PCPs at any point during the course of the one year intervention. During the visit, RN care managers and the PCPs will be prompted in CPRS to read a CPRS Research Note entered by a Health Coach. It will summarize the

interaction/discussion with the patient during the Baseline study visit, as well as any goals made or barriers discussed with the health coach (if the patient was randomized into the MTG Intervention arm). The PACT member may briefly counsel patients about lifestyle and weight. The PACT member will summarize this interaction in a specific CPRS note. Following the PCP visit, patients will be asked a series of questions about their experience during their baseline appointment (Pilot Phase 1) or at any of the follow-up research visits at the 3, 6, or 12 month mark (Pilot Phase 2). For all participants, we will measure intermediate and behavior change outcomes at 3-, 6- and 12-months via an in-person study visit. **Figure 3** shows a flow diagram of the study.

- **DESIGN**

Inclusion and Exclusion criteria of study participants: Criteria will include: aged 21-70 (this age range represents 96% of MOVE! participants) and a Body Mass Index of  $\geq 30\text{kg/m}^2$  or a Body Mass Index of  $\geq 25$  with two or more co-morbidities based on NIH weight loss guidelines. Individuals with a documented current history of substance abuse, diabetes, active psychosis, cognitive impairment, severe arthritis, valvular disease, cardiac arrhythmia, pregnancy, or other conditions limiting physical activity will be excluded. Patients who say they cannot read, do not have access to a telephone, and/or will not be available to be contacted at 3, 6, and 12 months for follow up will also be excluded.

Study Sites: The study will be conducted at the New York Harbor VA HCS. In 2009 and 2010, there were 16,000 total unique patients in primary care with 6,989 (44%) made by patients with a diagnosis of obesity. The Manhattan campus has 22 FTE primary care providers and 14 PACT teamlets with attending providers. [name], Director of Primary Care and other local PACT and MOVE! leaders have approved this study design and are supportive of PACT teamlet and patient participation in this study.

Time Frame: 12 months intervention, 2 year follow up.

Patient recruitment overview: We will recruit a consecutive sample of up to 160 overweight/obese patients (120 subjects who complete intervention assuming 25% patient dropout) from the VA primary care clinics. Since this is a pilot study, we may opt to stop recruitment earlier if study proves to be feasible and/or funding is obtained for a larger, cluster randomized efficacy study of the intervention. For Pilot Phase 1, we will obtain an electronic list of obese patients with appointments in the next month for participating providers and the RA will review charts for further eligibility. Lists of eligible patients will be sent to their respective primary care providers who will be asked to determine if any of the patients are medically ineligible to participate (e.g. have a condition where the PCP does not want the patient to engage in lifestyle behavior change). Potential participants will then be sent a letter from both the PI and their PCP describing the study and giving them the opportunity to opt out (i.e. request not to be contacted). Eligible participants will then be offered participation in the study via telephone. This recruitment strategy has been used by my mentor, [name], MPH, and was approved by the VA IRB.

For Pilot Phase 2, we will allow for participating PCPs to refer patients to the study. PCPs will be allowed to contact members of our team via phone or email with the contact information of patients they feel are a good fit for the study. As in the previously mentioned strategies, we will send letters to patients before contacting them by phone to explain the intervention, run through eligibility criteria, and review their medical charts. We will ask these PCP referred patients for permission to review their medical chart to determine medical eligibility. These patients will also be informed that they can opt out of receiving information by calling us.

For Pilot Phase 2, we will contact patients from an electronic list of overweight/obese patients who have been seen by their PCP in the past six months. From this list, we will mail out batches of recruitment letters (i.e. approximately 100 letters per week) to let patients know that they might be eligible to participate and that they can call us for more information at our study line. As in the aforementioned recruitment strategy, we will inform patients that they can opt out of receiving information by calling us. We will also highlight that we have to ask eligibility questions by phone to make sure they can participate. Importantly, before we call, we will e-mail their respective PCPs to ensure that patients are medically eligible. After PCP approval, we will contact patients by phone to explain the intervention, run through

eligibility criteria, and review their medical charts. We will ask all patients on the phone if it is permissible to review their medical chart to determine medical eligibility.

PCP and Health Coach Recruitment and Training Overview:

We will invite 3-10 PCPs to participate in the pilot study by presenting at staff meetings and via word of mouth. We will then ask the RN care managers and LPNs on their PACT teamlets if they would like to participate as well. Only those willing to participate will be included in the study and receive training. The training will be less than one hour and scheduled either one-on-one or in small groups so as not to interfere with their VA clinical or administrative duties. They will review the 5As and practice brief motivational interviewing to augment their previous VA training so they can support participants' weight management and lifestyle goals and address barriers. Based on our formative data, we will allow PACT teamlets to decide who will discuss goals/barriers with patients and outline possibilities.

We will train research assistants with either a bachelor's or master's degree to serve as health coaches. The health coaches will receive additional training based on a previous 5As curriculum I used in as part of an evidence-based intervention. The health coaches will receive 3-5 hours of training in small groups. They will practice counseling via role playing and videotape review.

Study Arms/Randomization: The first 10-12 participants will not be randomized—they will be recruited into the MTG intervention group only (see below) and outcomes for this group will be evaluated separately. The purpose of these first non-randomized participants is to ensure the feasibility of implementation prior to conducting the randomized portion of the pilot study. After screening patients for eligibility and obtaining consent, participants will be randomized (using a random number generator) to either the MTG intervention or Enhanced Usual Care.

*MTG Intervention group:* Participants will arrive to meet us in the 9th floor primary care area. After completing consenting materials and a Baseline Survey, participants will complete the MTG tool. They will then have a brief break and snack. After the break, they will work collaboratively with the Health Coach using tool-generated materials to modify their goals into SMART goals (specific, measurable, attainable relevant, and timely). The patient will then receive a binder containing an individualized report with a summary of their personalized advice, initial goals, and barriers and facilitators to weight loss. They will also receive a packet of MOVE! handouts tailored to their questionnaire responses. The Health Coach will also inform the patient of the resources available to them at the VA (e.g. MOVE, TeleMOVE!) that can assist them in achieving their goals. At the end of the visit, the Health Coach will enter a research note into the CPRS system detailing the patient's goals and other important information in the form of a provider report for the provider to review (generated by the MTG tool). This note will be attached to our administrative non-billable clinic, NYN PACT WEIGHT MGMT STUDY. For Pilot Phase 1, after health coaching, patients will meet with their PCP for their regularly schedule visit and afterwards complete an exit survey. For Pilot Phase 2, after health coaching, the patient will meet with the research team to complete an Exit Survey and then meet with their PCP during a regularly scheduled visit at any point during the course of the 1-year study. Based on information from the CPRS report generated by the health coach, the PCP will review lifestyle goals and conduct brief motivational interviewing to address potential barriers (3-5 minutes). The PACT member will summarize this interaction in a specific CPRS reminder. Over the 12 months of the intervention, the PACT teamlet will receive CPRS reminders to discuss the goals with the patients when they return for any PC visits. Research team members will contact the PCP directly should any serious issue arise while working a patient. Patients will follow up with VA resources if indicated/desired. Participants will return for separate 3, 6, and 12 month follow-up study visits to measure intermediate, behavior change, and weight outcomes.

- *Enhanced Usual Care:* Participants will arrive prior to scheduled PC visit and complete the same consenting materials and Baseline Survey as the intervention group. Instead of the completing the MTG tool and receiving health coaching, they will receive weight management handouts (Healthy Living Messages handouts and MOVE! handouts) as well as information about intensive weight management programs at the VA including MOVE!. For Pilot Phase 1, the patient will then meet with a PACT member (either the PCP or another participating PACT member) during their regularly scheduled PC visit and afterwards complete an Exit Survey. For Pilot Phase 2, the

patient will meet with their PCP at any point during the course of the study and afterwards complete an Exit Survey. Participants will follow-up with their PACT teamlets as needed when they return for their regularly scheduled PC visits. Patients will follow up with VA resources if indicated/desired. Enhanced Usual Care participants will return for separate 3, 6, and 12 month follow-up study visits to measure intermediate, behavior change, and weight outcomes.

- **COMPENSATION**

To compensate for travel and time spent completing survey measures and basic measurements, study participants will be given a cash voucher in the amount of 40 dollars for the Baseline study visit, 30 dollars for the 3 and 6 month study visits, and 60 dollars for the 12 month study visit. This proposed payment is reasonable and commensurate with the expected contributions of participants and is meant to provide additional incentives for participants to complete all 4 study visits. This amount of payment and the terms of the payment are included in the informed consent form. This payment is fair and appropriate and does not constitute undue pressure or influence, or coercion of, the prospective research participant to volunteer for or continue participation in the research study.

- **POTENTIAL BENEFIT/RISK**

Benefits:

- *Patients:* The patients who participate in the study will have the opportunity to receive weight management information, and potentially set lifestyle behavior change goals to improve their diet and increase physical activity, which may lead to weight loss and improved health outcomes. Even for patients who do not change their lifestyle behaviors, talking about these topics with trained researchers could serve as support or motivation to move them closer to doing so in the future.
- *Providers, RN Care Managers, and other VA employees:* VA employees who participate in the study may gain improved obesity-related knowledge and patient counseling skills, which could enhance their career, job performance, and satisfaction. Specifically, VA employees may have the opportunity to receive (additional) training in 5As weight management counseling and practice brief motivational interviewing. Training in these could help to facilitate and/or improve discussions around weight management and health behavior change with patients, as well as encourage the use of individualized techniques to improve diet and exercise and setting health behavior change goals with patients.

Risk:

- *Patients:* This research involves minimal risk for physical, psychological, social, and economic harm. The researchers understand that exploration of these topics and a persons' individual struggle with their weight can be emotionally charged for many people, particularly considering the stigma placed on obesity in our society. The researchers have been trained in order to effectively facilitate conversations on this sensitive topic and will seek to minimize any emotional discomfort you may feel during the study. Additionally, any potential behavior changes related to diet or exercise will be assessed and approved by properly trained individuals including select research staff, the Primary Investigator, and health professionals. Patients will be encouraged to slowly increase their physical activity under the supervision of their PCP. While there is always the risk of injury from starting or increasing physical activity, the benefits usually outweigh potential harms. We will monitor patients for adverse events.
- *VA employees:* This research involves minimal risk for physical, psychological, social, and economic harm.

- **MEASUREMENTS**

Assessment will occur at the following time points:

- A. Baseline study visit: Baseline survey and basic physical measurements (weight, height, waist circumference)
- B. In-person follow-up study visits at 3, 6 and 12 months: Follow-up in-person questionnaire and basic physical measurements (weight, height, waist circumference)

- C. Follow-up telephone calls (only patients in MTG intervention): Follow-up telephone questionnaire
- D. Chart review: This will occur periodically to assess MOVE! attendance, PACT teamlet visits (documentation of weight management-related conversations), and medical co-morbidities. Outcomes will be assessed through chart review up to 2 years after the baseline visit.

Baseline Data: Prior to the intervention, patients will receive a Baseline survey. To evaluate recruitment for the intervention, baseline data including socio-demographic information, perceived health status, health literacy, perceived environmental factors, and depression will be collected. Co-morbidities will be determined through chart review of the electronic medical record. We will also collect health-related attitudes, beliefs, and baseline behaviors.

Weight & Height: Study personnel will obtain patient weight measurements using a standardized protocol which includes; 1) weighing before eating without shoes or heavy garments using a digital scale that will be calibrated monthly; 2) measuring height using the primary care clinic stadiometer and rounded to the nearest half inch, at each study time point (Baseline, 3, 6, and 12 months).

Waist Circumference: Waist circumference will be measured using procedures adapted from National Health and Nutrition Examination Survey (NHANES). Study personnel will use measuring tape to the nearest 0.1cm at the high point of the iliac crest at minimal respiration. This will be measured at baseline, 3, 6, and 12 months.

Feasibility: We will use process measures (from direct observation, to determine the feasibility of implementing the MTG intervention at the initial visit. Data on time to complete the MTG tool, number and types of goals made, number of patients reporting that their PACT teamlets engaged in goal setting conversations, number of reminders completed by the PACT teamlets, time spent doing the intervention, the impact of the intervention on workflow (physician and RN Care Manager report, qualitative interviews) will be collected. At 3 and 6 months into the study period, participating PACT teamlet staff will complete an attitudes survey based on one we have used previously pertaining to intervention implementation. We will also perform qualitative interviews with RN Care Managers and providers. We will use chart review to note the number of times patients in the telephone support arm actually receive telephone counseling.

Acceptability: We will collect data on patient satisfaction with the intervention and the overall visit using patient and provider surveys. We will conduct interviews with participating providers and RN Care Managers to obtain qualitative data on acceptability.

Intermediate Outcomes: Our intermediate outcomes are based on the theory of planned behavior where motivation and intention to perform a behavior, mediated by self-efficacy, predict behavior change. These constructs will be measured using previously used items that have been adapted for our survey measures by adding other elements of the Theory of Planned Behavior including behavioral beliefs, attitudes, subjective norms, and perceived behavioral control. We will also assess goal attainment at 3, 6, 12 months.

Behavioral Outcomes: We will assess diet and physical activity behaviors at baseline and again at 3, 6, and 12 months. Our main dietary outcomes will be servings of fruits and vegetables, fat intake, refined carbohydrates, and sweetened beverage intake via surveys. A subset of up to 20 participants will complete 24-hour dietary recalls, and this will allow us to assess total energy intake and energy density in this subgroup. Physical activity outcomes will be changes in duration and intensity. We will use chart review to evaluate attendance to TeleMOVE! or MOVE! (# of sessions) pre- and post-baseline visit and 3, 6, and 12 months post- intervention.

Treatment Fidelity: During patient surveys conducted after the patient sees the primary care provider, we determine whether patients recall reviewing goals and receiving obesity-related counseling from the provider. We will also audiotape up to 5 Baseline visits with each provider to evaluate the quality of counseling around patient goals and potential barriers to achieving them. Finally, we will do detailed chart reviews using a chart abstraction tool to monitor how often providers see patients and document goal-setting discussions during subsequent visits after the index visit.

Data Storage/Security

- *Research Activities:* The following will all take place in private room at the Manhattan VA with the PI and/or research staff – filling in consent forms, using MTG tool, receiving weight management information, receiving weight management counseling, completing survey measures.
- *Storage of data:* All written data will be kept in locked filing cabinets in a locked room only accessible by the PI and approved study personnel and all electronic data (including survey responses, audio files, and responses to online tool) on secure local VA servers and only accessible on VA password protected computers by the PI and study personnel. Original audio files will be removed from recorders. The data key link will be maintained as a password-protected Excel datasheet on a secure VA Harbor computer within a locked VA Harbor office by the PI, and destroyed upon completion of the final study dataset. The data key link will be kept separate from all survey responses. Only study investigators will perform data entry, access either the surveys or datasets, or perform any analysis of the dataset.
- *Transcription:* For transcription of audio files, files will be sent as encrypted files through the secure server to the VA-contracted transcription company, Transcription Outsourcing, LLC. Transcripts will be de-identified by leaving all identifiable information out of the transcript and using only a unique coded identifier generated by the Principal Investigator. This unique identifier will not use any identifying information (i.e. it will not be generated using the subject's social security number, name, etc.) Recorded information will be transferred to Transcription Outsourcing via a HIPAA-compliant web portal using a VA computer. The transcripts will then be stored and analyzed on a VA secure server. This transcription procedure was approved by the IRB previously (MIRB 01333) under the consultation of the ISO and PO.
- *The MTG tool:* The MTG tool uses a web-interface to ask health questions and collect the data in order to deliver tailored advice. This website will be hosted on either a hired private programmer's server (approved research personnel) or an NYU server. In both cases, Data Use Agreements have been setup with both parties and the VA to protect ownership and use of collected coded data. Data will be regularly migrated from either server (private programmer or NYU) to the VA server via encrypted USB drive. This data storage procedure was approved by the IRB previously (MIRB 01333) under the consultation of the ISO and PO.

Other Quality Control Procedures: The study staff will meet biweekly for the duration of the study to review patient recruitment and data collection procedures to ensure standardization. Research assistants will send reminders to Health Coaches when it is time to call patients in the telephone support arm. To monitor for and address unanticipated adverse events, there will be discussions during meetings with research staff, PI, mentors of PI, and providers/VA staff.

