5As Intervention Development: As part of our Formative Phase I studies, we conducted Veteran focus groups and interviews with key VA PACT and MOVE! staff to assess a proposed brief intervention based on the 5As where patients use an online tool to create health goals and then bring these goals and advice discussed with their health coach to members of the PACT teamlets during their primary care visit.). Participants were also asked about their experiences with goal setting, weight management, and technology. Both Veterans and VA staff held positive views toward the use of goal setting for healthy behavior change and stressed the importance of social support in achieving goals. Veterans and staff appreciated that the intervention would provide individualized counseling from the healthcare team to achieve goals. Veterans did not want technology to replace human support. Physicians and nurses felt that time constraints would be a barrier to implementation, indicating that they could not spend more than 3-5 minutes on weight management. As a result, the revised intervention will use health coaches to provide support for the online tool and initial counseling about weight loss and lifestyle goals to allow the healthcare team to focus their time on brief counseling to address barriers and endorse goals.

Based on this formative work, we have developed the following components of the intervention and measures: (subject to change based on the results from our ongoing pilot testing):

- Pre-/Post-surveys: We developed survey measures to be taken before and after the MTG tool to gather demographic information, as well as assess computer use, knowledge/participation in MOVE! programs, experiences with PACT, health literacy, their social/physical environment, quality of life, social support, level of patient activation, motivation to lose weight, self-efficacy, diet, and physical activity behaviors. Most of the question items are taken from validated measures.

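### In Pilot Phase 2 the Exit Survey comes before the PCP visit in the MTG arm and after it in the Enhanced Usual Care arm

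*Combined protocol and SAP*

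**What the plan says.** Under Study Arms/Randomization, each arm's description gives its order of events by phase.

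- **MTG, Phase 1:** "patients will meet with their PCP for their regularly schedule visit and afterwards complete an exit survey".
- **MTG, Phase 2:** "after health coaching, the patient will meet with the research team to complete an Exit Survey and then meet with their PCP". That PCP visit may fall at any time in the study year.
- **Enhanced Usual Care, Phase 1:** the participant sees the PCP or another PACT member at the scheduled visit and takes the Exit Survey after it.
- **Enhanced Usual Care, Phase 2:** the "patient will meet with their PCP at any point during the course of the study and afterwards complete an Exit Survey".

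The Overview of Research Design and Methods agrees with the Phase 1 order and applies it to everyone: "In Pilot Phase 1, participants will meet with their PCP during their regularly scheduled visit before taking an exit survey". Of Phase 2 it says that "the methods of recruitment and sequence of events will be modified to maximize ease and enrollment". It also describes a set of questions asked once the PCP has been seen. In Phase 1 these concern the baseline appointment; in Phase 2 they are asked at the 3, 6 or 12 month research visits. That text names neither the Exit Survey nor an arm.

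The list of assessment time points under Measurements does not include the Exit Survey. The Statistics Analysis Plan begins by summarizing all variables overall and by randomized arm. It then compares intermediate, behavioral and weight outcomes between arms at 3, 6 and 12 months. It does not mention the Exit Survey.

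**The concern.** A questionnaire that is to be read across randomized arms should be taken at the same point in each. Here the Phase 2 survey falls on opposite sides of the PCP visit. That visit is itself an occasion for weight counseling, so it could change how a participant answers. A difference between arms on such an item could then reflect whether the PCP had already been seen, or how long ago baseline was, and not the MTG intervention.

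This could reach three parts of the plan. Treatment Fidelity relies on patient surveys taken after the PCP visit, to learn whether goals and counseling are recalled. Feasibility counts patients who report goal-setting conversations with their teamlet. Acceptability uses patient satisfaction surveys, and a between-arm look at acceptability is part of the Primary Aim.

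**Working it through.** No figure in the plan bears on this point, so the check is a comparison of texts.

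**Step 1. Set the four groups side by side** (2 arms × 2 phases = 4).

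| Arm | Phase | Exit Survey relative to the PCP or PACT visit |
|---|---|---|
| MTG | 1 | After |
| Enhanced Usual Care | 1 | After |
| MTG | 2 | Before |
| Enhanced Usual Care | 2 | After |

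The survey follows the visit in 3 of the 4 groups and precedes it in 1. The arms match in Phase 1 and not in Phase 2.

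**Step 2. Look for text that reconciles or justifies this.**

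- The Overview's remark on a modified sequence concerns a change between phases. It gives no reason for a difference between arms.
- The Overview's questions after the PCP visit are, in Phase 2, asked "or at any of the follow-up research visits at the 3, 6, or 12 month mark (Pilot Phase 2"). They may be a separate instrument. They could also be the control arm's Exit Survey, but the text does not say so, and on that reading the MTG order would still be different.
- The Compensation section counts 4 study visits, and Measurements places them at baseline, 3, 6 and 12 months. None is tied to a Phase 2 PCP visit, so the arm description alone does not tell staff at which contact a control takes the survey.
- Under Preliminary Studies, the item on pre- and post-surveys says: "We developed survey measures to be taken before and after the MTG tool to gather demographic information". It does not say whether the later survey is the Exit Survey, and controls do not use the tool.

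None of these settles the timing.

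**Step 3. Follow the text as written into a by-arm summary of Phase 2.**

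- *PCP exposure:* MTG answers are given before the study PCP visit, control answers after one.
- *Time since baseline:* MTG participants answer straight after coaching, which belongs to the Baseline visit. Controls answer after a visit that may fall at any point in the study. The gap could be short, because the control description opens with participants arriving ahead of a scheduled primary care visit, or it could be long.
- *Missing data:* a control who has no PCP visit has no Exit Survey. An MTG participant's survey does not depend on having one.

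**Step 4. Pooling the phases.** MTG responses would mix post-PCP (Phase 1) with pre-PCP (Phase 2). Control responses would all be post-PCP.

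**Step 5. Which stated measures are touched.** As written, the Phase 2 Exit Survey cannot supply recall of counseling at the study PCP visit in the MTG arm, because that visit has not yet happened. The Overview's follow-up questions can supply it. Satisfaction is touched only if its items are on the Exit Survey, which the document does not say.

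**Step 6. Size.** The share of participants enrolled in Phase 2, the survey's items and the effect of a PCP visit on any item are all unstated. Any number for the bias would only restate assumed values, so none is given.

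**The case against.** The strongest reply is that this is a slip of wording with no analysis resting on it. The control arm's Phase 2 sentence may simply have kept the Phase 1 order. If staff in fact give the survey at the same point in both arms, there is no confounding. The Statistics Analysis Plan names no test of Exit Survey items. The fidelity and feasibility measures also have other sources: the Overview's follow-up questions, chart review, audiotaped Baseline visits, completed reminders and provider interviews.

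Much of this stands. Nothing shows that a difference by arm was intended, and no stated endpoint is shown to be lost. What does not fall away is the conflict between the two arm descriptions, which are the instructions staff would follow. The plan also summarizes all variables by arm, so the responses would be set side by side even without a formal test.

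A reader might also count the Overview as a third conflicting version of the Exit Survey's timing. The text does not support that: it speaks of questions about the participant's experience, never names the Exit Survey, and may complement both arm descriptions.

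**Conclusion.** The point holds as a minor one. The Phase 2 descriptions of the two arms place the Exit Survey on opposite sides of the PCP visit, and no other section reconciles or justifies this. Confidence in the mismatch is high. The consequence is conditional: it assumes that the Exit Survey is one instrument in both arms, that staff follow the text as written, and that its items are summarized by arm or pooled across phases. The size and direction of any bias are unknown.

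Two stronger readings are tempting and are not supported. One is that the Primary Aim's acceptability comparison is biased; the document does not say that acceptability items are on this survey. The other is that the trial's main comparisons are compromised; weight, behavioral and intermediate outcomes are measured at 3, 6 and 12 months in both arms and do not depend on the Exit Survey.

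**What to change.** Reconcile the two arm descriptions so that the Phase 2 Exit Survey is given at the same point relative to baseline and to the PCP visit in both arms. The end of the Baseline study visit is one workable choice. It needs no extra contact and does not depend on a PCP visit taking place.

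Collect the items on PCP counseling, goal recall and goal-setting conversations in both arms through the follow-up questions that the Overview already places at 3, 6 or 12 months, and say that those questions are the source for these measures.

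Do not pool pre-PCP and post-PCP Exit Survey responses. If the Phase 2 survey moves to the Baseline visit in both arms, Phase 1 remains post-PCP, so report the phases separately.

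The cost is protocol wording and a change in when an existing survey is given, with no new visit or staff. The downside of the baseline option is that the Phase 2 Exit Survey would not cover the PCP visit, and participants would be asked to recall PCP counseling later.
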